## 1. INTRODUCTION

This supplemental SAP (sSAP) is a companion document to the protocol. In addition to the information presented in the protocol SAP which provides the principal features of confirmatory analyses for this trial, this supplemental SAP provides additional statistical analysis details/data derivations and documents modifications or additions to the analysis plan that are not “principal” in nature and result from information that was not available at the time of protocol finalization.

## 2. SUMMARY OF CHANGES

sSAP Version #	Protocol Amendment #	sSAP Section # and Name	Description of Change	Brief Rationale
03	04	4.1.1 China-specific Requirements	Added a clarification for PRO analysis for the China subpopulation	To clarify that separate PRO analysis for the China subpopulation is not applicable

### 3. ANALYTICAL AND METHODOLOGICAL DETAILS

### 3.1 Statistical Analysis Plan Summary

Key elements of the statistical analysis plan are summarized below; the comprehensive plan is provided in Sections 3.2-3.12.

Study Design Overview	A Phase 3 study of MK-4280A Versus Standard of Care in Previously Treated Metastatic Colorectal Cancer.
Treatment Assignment	Approximately 432 participants will be randomized in a 1:1 ratio between 2 treatment groups: (1) the MK-4280A arm (Arm A) and (2) the standard of care (regorafenib or TAS-102) arm (Arm B). Stratification factors are: Geographic region (Asia Pacific; EMEA/Americas), presence of liver metastasis (Yes, No) and time from initial diagnosis of metastatic disease to randomization ( $\geq 18$ months, $< 18$ months). This is an open-label study.
Analysis Populations	Efficacy: ITT Safety: APaT
Primary Endpoint(s)	Overall survival
Key Secondary Endpoints	Progression-free survival per RECIST 1.1 as assessed by BICR. Objective response rate per RECIST 1.1 as assessed by BICR.
Statistical Methods for Key Efficacy/Immunogenicity/ Pharmacokinetic Analyses	The primary hypothesis testing for OS and secondary hypothesis testing for PFS will be evaluated by comparing the experimental group to the control group using a stratified log-rank test. The HR will be estimated using a stratified Cox regression model. Event rates over time will be estimated within each treatment group using the Kaplan-Meier method. The stratified M&N method with strata weighted by sample size will be used for secondary hypothesis testing of ORR [Miettinen, O. and Nurminen, M. 1985].
Statistical Methods for Key Safety Analyses	For analyses in which 95% CIs will be provided for between-treatment differences in the percentage of participants with events, these analyses will be performed using the M&N method [Miettinen, O. and Nurminen, M. 1985].
Interim Analyses	
Efficacy
 
One interim analysis is planned in this study. Results will be reviewed by an eDMC. Details are provided in Section 3.7.
 
 
• CCI
 
 
Safety
 
CCI

	will review safety data periodically in the study. Details will be specified in the DMC charter.
Multiplicity	The overall type I error over the primary and secondary hypotheses is strongly controlled at 2.5% (1-sided), CCI [REDACTED] By using the graphical approach of Maurer and Bretz [Maurer, W. and Bretz, F. 2013], if one hypothesis is rejected, the alpha will be shifted to other hypotheses.
Sample Size and Power	CCI [REDACTED]
Abbreviations: APaT = all participants as treated; BICR = blinded independent central review; CI = confidence interval; DMC = data monitoring committee; eDMC = external data monitoring committee; FAS = full-analysis set; HR = hazard ratio; ITT = intent to treat; M&N = Miettinen and Nurminen; ORR = objective response rate; CCI [REDACTED]; PFS = progression free survival; SOC = standard of care	

### 3.2 Responsibility for Analyses/In-House Blinding

The statistical analysis of the data obtained from this study will be the responsibility of the Clinical Biostatistics department of the Sponsor.

The Sponsor will generate the randomized allocation schedule(s) for study treatment assignment as appropriate in this protocol, and the allocation will be implemented in IRT.

Although the study is open-label, analyses or summaries generated by randomized intervention assignment, or actual intervention received will be limited and documented.

Blinding issues related to the planned interim analyses are described in Section 3.7.

### 3.3 Hypotheses/Estimation

Objectives and hypotheses of the study are stated in Section 3 of the protocol.

### 3.4 Analysis Endpoints

Efficacy and safety endpoints that will be evaluated are listed below.

#### 3.4.1 Efficacy Endpoints

##### Primary

- Overall Survival**

OS is defined as the time from randomization to death due to any cause.

## **Secondary**

- **Progression-free survival**

PFS is defined as the time from randomization to the first documented disease progression per RECIST 1.1 by BICR or death due to any cause, whichever occurs first.

- **Objective Response Rate**

The ORR is defined as the percentage of participants who achieve a confirmed CR or PR per RECIST 1.1 as assessed by BICR.

- **Duration of Response**

For participants who demonstrate confirmed CR or PR, duration of response is defined as the time from the first documented evidence of CR or PR until disease progression or death due to any cause, whichever occurs first.

### **3.4.2 Safety Endpoints**

Safety and tolerability will be assessed by clinical review of all relevant parameters, including AEs, SAEs, fatal AEs, laboratory tests. Furthermore, specific events will be collected and designated as ECIs as described in Section 8.4.7 of the protocol.

### **3.4.3 PRO Endpoints**

- Change from baseline in EORTC QLQ-C30 global health status/quality of life scores (QoL), physical functioning and appetite loss and EORTC QLQ-CR29 bloating scores for MK-4280A versus standard of care
- Time to confirmed deterioration (TTD) in EORTC QLQ-C30 global health status/QoL, physical functioning and appetite loss and EORTC QLQ-CR29 bloating scores for MK-4280A versus standard of care

Based on prior literature (Bjordal, et al., 2000; Osoba D, 1998 [Osoba, D., et al 1998]; King, 1996 [King, M. T. 1996]), a 10 points or greater worsening from baseline for each scale represents a clinically relevant deterioration for EORTC. TTD is defined as the time from baseline to the first onset of a 10 or more points deterioration from baseline with confirmation at the subsequent visit of a 10 or more points deterioration from baseline.

- **CCI**  
[REDACTED]
- Overall improvement / stability + improvement in EORTC QLQ-C30 global health status / QoL, physical functioning and appetite loss and EORTC QLQ-CR29 bloating scores:

The assessment for possible PRO response at a time point considering subsequent confirmation is defined as follows:

Assessment Category at a time point (one analysis visit)	Change from baseline at a time point (one analysis visit)	Change from baseline at the subsequent time point (the next consecutive analysis visit)
Improvement	score improved from baseline by $\geq 10$ points	score improved from baseline by $\geq 10$ points
Stability	score improved from baseline by $\geq 10$ points	score improved or worsened from baseline by $< 10$ points
	score improved or worsened from baseline by $< 10$ points	score improved or worsened from baseline by $< 10$ points
	score improved or worsened from baseline by $< 10$ points	score improved from baseline by $\geq 10$ points
Worsening	score worsened from baseline by $\geq 10$ points	not required
Unconfirmed	A time point assessment that doesn't meet any of the above criteria.	

The overall improvement is defined as the best observed PRO response that is an improvement among all post-baseline assessments by timepoint. The overall improvement + stability is defined as the best observed PRO response that is an improvement or stability among all post-baseline assessments by timepoint.

Changes from baseline in EORTC QLQ-C30 scores will also be interpreted according to recent subscale-specific guidelines, which indicate that clinically meaningful differences vary by scale (Cocks et al., 2012 [Cocks, K., et al 2012]).

### 3.5 Analysis Populations

CCI

#### 3.5.1 Efficacy Analysis Populations

The ITT population will serve as the primary population for the analysis of efficacy data in this study. The ITT population consists of all randomized participants. Participants will be analyzed in the treatment arm to which they are randomized. Details of the approach to handling missing data are provided in Section 3.6.1.4.

#### 3.5.2 Safety Analysis Populations

Safety Analyses will be conducted in the APaT population, which consists of all randomized participants who received at least one dose of study treatment. Participants will be included in the treatment group corresponding to the study treatment they actually received for the analysis of safety data using the APaT population. This will be the treatment group to which they are randomized except for participants who take incorrect study treatment for the entire treatment period; such participants will be included in the treatment group corresponding to the study treatment actually received.

At least one laboratory or vital sign measurement obtained after at least one dose of study treatment is required for inclusion in the analysis of the respective safety parameter. To assess change from baseline, a baseline measurement is also required.

### **3.5.3 PRO Analysis Populations**

The PRO analyses are based on the PRO FAS population, defined as all randomized participants who have at least one PRO assessment available for the specific endpoint and have received at least one dose of the study intervention. Participants will be analyzed in the treatment group to which they are randomized.

## **3.6 Statistical Methods**

Statistical testing and inference for safety analyses are described in Section 3.6.2. Efficacy results that will be deemed to be statistically significant after consideration of the Type I error control strategy are described in Section 3.8, Multiplicity. Nominal p-values may be computed for other efficacy analyses, but should be interpreted with caution due to potential issues of multiplicity, sample size, etc.

### **3.6.1 Statistical Methods for Efficacy Analyses**

This section describes the statistical methods that address the primary and secondary efficacy objectives. Methods related to exploratory objectives will be described in the supplemental SAP.

The stratification factors used for randomization (Section 6.3.2 of the protocol) will be applied to all stratified analyses, in particular, the stratified log-rank test, stratified Cox model, and stratified M&N method [Miettinen, O. and Nurminen, M. 1985]. CCI

CCI

CCI

### 3.6.1.1 Overall Survival

The non-parametric Kaplan-Meier method will be used to estimate the survival curves. The treatment difference in survival will be assessed by the stratified log-rank test. A stratified Cox proportional hazard model with Efron's method of tie handling will be used to assess the magnitude of the treatment difference (ie, the HR). The HR and its 95% CI from the stratified Cox model with a single treatment covariate will be reported. Participants without documented death at the time of analysis will be censored at the date the participant was last known to be alive.

The proportional hazards assumption on OS may be examined using both graphical and analytical methods if warranted. The log [-log] of the survival function vs. time for OS will be plotted for the comparison between MK-4280A and the control arm. If the curves are not parallel, indicating that hazards are not proportional, supportive analyses may be conducted to account for the possible non-proportional hazards effect associated with immunotherapies: for example, using the Restricted Mean Survival Time method (Finkelstein DM, 1986 [Finkelstein, D. M. 1986]).

The RMST is simply the population average of the amount of event-free survival time experienced during a fixed study follow-up time. This quantity can be estimated by the area under the Kaplan-Meier curve up to the follow-up time. The clinical relevance and feasibility should be taken into account in the choice of follow-up time to define RMST (e.g., near the last observed event time assuming that the period of clinical interest in the survival experience is the whole observed follow-up time for the study, but avoiding the very end of the tail where variability may be high); a description of the RMST as a function of the cutoff time may be of interest. The difference between two RMSTs for the two treatment groups will be estimated and 95% CI will be provided.

A sensitivity analysis may be performed based on the MaxCombo test with logrank FH (0, 1), FH (1, 1) at the final analysis of OS to account for the potential loss of power with logrank test when the proportional hazard assumption is violated.

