In order to evaluate the robustness of the PFS endpoint per RECIST 1.1 by BICR, 2 sensitivity analyses with different sets of censoring rules will be performed. The first sensitivity analysis follows the intention-to-treat principle. That is, PDs/deaths are counted as events regardless of missed study visits or initiation of new anticancer therapy. The second sensitivity analysis considers initiation of new anticancer treatment or discontinuation of treatment due to reasons other than complete response, whichever occurs later, to be a PD event for participants without documented PD or death. If a participant meets multiple criteria for censoring, the censoring criterion that occurs earliest will be applied. The censoring rules for the primary and sensitivity analyses are summarized in [Table 1](#).

Table 1 Censoring Rules for Primary and Sensitivity Analyses of PFS

Situation	Primary Analysis	Sensitivity Analysis 1	Sensitivity Analysis 2
PD or death documented after $\leq 1$ missed disease assessment, and before new anticancer therapy, if any	Progressed at date of documented PD or death	Progressed at date of documented PD or death	Progressed at date of documented PD or death
PD or death documented immediately after $\geq 2$ consecutive missed disease assessments, or after new anticancer therapy	Censored at last disease assessment prior to the earlier date of $\geq 2$ consecutive missed disease assessment and new anticancer therapy, if any	Progressed at date of documented PD or death	Progressed at date of documented PD or death
No PD and no death; and new anticancer treatment is not initiated	Censored at last disease assessment	Censored at last disease assessment	Progressed at treatment discontinuation due to reasons other than complete response; otherwise censored at last disease assessment if still on-study treatment or completed study treatment
No PD and no death; new anticancer treatment is initiated	Censored at last disease assessment before new anticancer treatment	Censored at last disease assessment	Progressed at date of new anticancer treatment
PD=progressive disease; PFS=progression-free survival.			

The proportional hazards assumption on PFS may be examined using the same approach as OS, and supportive analyses may be conducted when the proportional hazard assumption is violated: for example, using the Restricted Mean Survival Time method (Finkelstein DM, 1986 [Finkelstein, D. M. 1986]).

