### 3.9 Sample Size and Power Calculations

The study will randomize 432 participants in a 1:1 ratio into the MK-4280A arm (Arm A) and the standard of care arm (Arm B). OS is the primary endpoint for the study, with PFS and ORR as the key secondary endpoints.

For the OS endpoint, based on a target number of 386 events and 1 IA at approximately 80% of the target number of events, the study has approximately 93.5% power to detect a HR of 0.7 at the initially allocated  $\alpha=0.025$  (1-sided).

For the PFS endpoint, based on a target number of 419 events at the IA (final PFS analysis), the study has approximately 99% power to detect a HR of 0.65 at the reallocated  $\alpha=0.0125$  (1-sided) if only OS hypothesis is rejected.

Based on the 432 participants with at least approximately 10 months of follow-up, the power of the ORR testing at the reallocated  $\alpha=0.0125$  (1-sided) if only OS hypothesis rejected is approximately 97% to detect a 10-percentage point difference between an underlying 2% ORR in the control arm (Arm B) and a 12% ORR in the experimental arm (Arm A).

Note that the above OS and PFS power calculations are based on a constant HR assumption.

[figure not shown]
Based on CORRECT, RE COURSE, and SUNLIGHT studies (Section 4.2.1.1 of protocol), the above sample size and power calculations for OS and PFS assume the following:

- OS follows an exponential distribution with a median of 7.5 months for the control group.
- PFS follows an exponential distribution with a median of 2 months for the control group.
- Enrollment period of 12 months with enrollment ramp-up over first 2 months.
- An annual dropout rate of 2% and 5% for OS and PFS, respectively
- A follow-up period of 22 and 10 months and for OS and PFS, respectively, after the last participant is randomized.

The sample size and power calculations were performed using R (“gsDesign” package).

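### The supportive RMST difference for OS and PFS is described without the three randomization factors, so its 95% CI is slightly conservative if those factors are prognostic

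*SAP*

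**What the plan says.** Section 3.1 stratifies randomization by region, liver metastasis and time since metastatic diagnosis: three binary factors, eight strata. Section 3.6.1 applies these factors to all analyses called stratified, "in particular, the stratified log-rank test, stratified Cox model, and stratified M&N method". Redacted text follows that sentence. The primary OS and PFS tests and Cox models (Sections 3.6.1.1 and 3.6.1.2) are stratified.

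For non-proportional hazards, Section 3.6.1.1 names RMST as an example of a supportive analysis and describes the estimator: "This quantity can be estimated by the area under the Kaplan-Meier curve up to the follow-up time". The difference between the two arms is reported with a 95% CI. Strata are not mentioned. For PFS, Section 3.6.1.2 says that "supportive analyses may be conducted when the proportional hazard assumption is violated", again with RMST as the example.

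A second optional analysis covers OS only: "A sensitivity analysis may be performed based on the MaxCombo test with logrank FH (0, 1), FH (1, 1) at the final analysis of OS". The text does not say whether that test is stratified.

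Section 3.6 treats p-values outside the Section 3.8 testing strategy as nominal.

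**The concern.** When randomization is stratified on prognostic factors, the arms are balanced on them by design, and the true sampling variance of the RMST difference is smaller than the plain Kaplan-Meier variance formula implies. An analysis that ignores the factors then reports an interval wider than the design warrants.

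The plan handles this elsewhere. It names stratified methods for OS, PFS, ORR, time to deterioration and PRO improvement rates, and it puts the factors into the longitudinal PRO model as covariates. For the China subpopulation it says explicitly that methods are unstratified. The RMST description follows neither pattern.

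At stake is some precision in an analysis that would be consulted if the curves showed a delayed effect. Validity is not at stake.

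**Working it through.** **Plan's own figure first.** Inputs from Sections 3.1 and 3.9: "The overall type I error over the primary and secondary hypotheses is strongly controlled at 2.5% (1-sided"; "The study will randomize 432 participants in a 1:1 ratio"; "based on a target number of 386 events and 1 IA at approximately 80% of the target number of events"; "approximately 93.5% power to detect a HR of 0.7 at the initially allocated" alpha. With Lan-DeMets O'Brien-Fleming spending at an information fraction of 0.80, the interim bound is Z = 2.2504 (p = 0.0122) and the final bound Z = 2.025 (p = 0.0214). Power at HR 0.7 is 0.8115 at the interim (stated 0.8123) and 0.9346 at the final analysis (stated 0.9350). The design inputs are therefore understood correctly. The SAP states no figure for RMST.

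**Inputs not in the SAP (assumptions).** Prevalence: liver metastasis 70%, less than 18 months since metastatic diagnosis 35%, Asia Pacific 40%. Prognostic hazard ratios (liver/time/region): 1.5/1.3/1.0, 1.8/1.4/1.1 and 2.0/1.5/1.2. Truncation time τ = 21 months. The overall control median is held at the plan's 7.5 months, and the within-stratum treatment HR at 0.7.

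**Step 1: share of variance explained by the strata.** In a stratum with exponential hazard λ,
- E[min(T,τ)] = (1 − e^(−λτ))/λ
- E[min(T,τ)²] = (2/λ²)·(1 − e^(−λτ)(1 + λτ))

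The share is R² = Var(E[min(T,τ) | stratum]) / Var(min(T,τ)), averaged over the arms. In the strongest case, control gives 5.30/52.2 = 10.1% and experimental 4.88/57.8 = 8.4%, so R² = 9.3%. The other two cases give 3.5% and 6.6%.

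**Step 2: excess in the plain standard error.** The ratio is k = 1/√(1 − R²):
- 1/√0.965 = 1.018
- 1/√0.934 = 1.035
- 1/√0.907 = 1.050

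The plain SE is about 1.8%, 3.5% and 5.0% too large.

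**Step 3: cost in power.** If adjusted power is P, plain power is Φ(z_P − 1.96(k − 1)). At k = 1.05 the shift is 1.96 × 0.05 = 0.098. The loss is 3.9 points at P = 50%, 3.5 at P = 70% and 1.8 at P = 90%. At P = 70%, the smaller values of k lose 1.2 and 2.4 points. Overall the range is about 0–4 points.

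**Step 4: simulation of adjusted RMST.** There were 1,200 trials per scenario, with τ = 21, HR 0.75 and inverse-probability-of-censoring-weighted (IPCW) regression on the three factors. Power rose from 70.3% to 71.1%, 68.0% to 70.3% and 66.8% to 69.7%. Each figure has a Monte Carlo SE of about √(0.7 × 0.3/1200) = 1.3 points, so the closed form above is the firmer evidence. With non-prognostic factors the two methods gave 72.9% and 72.7%, which is no material difference.

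**Step 5: separate simulation of the plain interval.** There were 2,500 trials per scenario, with τ = 24, HR 0.7, permuted blocks of 4 and a data cut at month 33. Assumed prevalences were 70/40/40% and prognostic HRs 1/1/1, 1.5/1.3/1.1 and 2.0/1.6/1.2.

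| Factors | Plain SE | Sampling SD of plain estimate | Ratio |
|---|---|---|---|
| None | 0.778 | 0.782 | 0.995 |
| Moderate | 0.785 | 0.772 | 1.017 |
| Strong | 0.796 | 0.758 | 1.050 |

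The point estimate barely moves with stratification (strong: 2.377 against 2.375 months). Under the null, plain RMST rejects at 2.5%, 1.8% and 2.0% one-sided, so the error is on the conservative side.

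This simulation also tried a size-weighted average of within-stratum Kaplan-Meier areas. Its SE fell 2–3% short of its own sampling SD (0.766/0.783 = 0.978; 0.757/0.774 = 0.978; 0.739/0.760 = 0.972). That favours covariate regression over splitting the data into eight strata.

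**Step 6: MaxCombo in the same simulation (power, unstratified against stratified).**

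| Factors | Proportional hazards | 4-month delay |
|---|---|---|
| None | 90.6% / 89.3% | 85.0% / 82.9% |
| Moderate | 90.0% / 90.2% | 82.8% / 81.5% |
| Strong | 85.1% / 90.1% | 76.5% / 80.0% |

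The sign depends on the assumed prognostic strength.

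**The case against.** The plain RMST difference is a legitimate marginal estimate, and Section 3.6.1.1 itself describes RMST as a population average. The wording on the Kaplan-Meier area is permissive, every prognostic input is assumed, and the analysis is optional and without alpha. All of that stands. It limits the point to a small gain in precision, but the described estimator still leaves out factors the design has balanced.

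Three stronger readings are tempting, and the SAP does not support them:

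- **That MaxCombo drops the strata and is therefore less powerful.** The SAP is silent on strata for this test, and redacted text follows the general stratification sentence in Section 3.6.1. Stratifying helps only under strong assumed factors, makes no clear difference under moderate ones, and loses 1–2 points if the factors are not prognostic.
- **That these are the only analyses available under non-proportional hazards.** RMST is given as an example, so the list is open.
- **That adding strata would make RMST like-for-like with the log-rank test.** A mean difference and a hazard ratio are different summaries, and a disagreement would still have more than one explanation.

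The absence of a numeric truncation time is a separate matter. Section 3.6.1.1 gives guidance on the choice and does not direct picking the most favourable cutoff.

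**Conclusion.** The point holds as a minor improvement. As described, the RMST difference is unadjusted for the three randomization factors, for OS and by reference for PFS. It is valid, and its 95% CI is about 0–5% too wide, equivalent to about 0–4 points of RMST power. Those ranges rest on prognostic strengths and prevalences that the SAP does not give, on exponential survival within strata, and on truncation at 21–24 months. They were worked out for OS only; no separate PFS calculation was made. Adjustment brings no material loss if the factors are not prognostic. The Section 3.8 tests of OS, PFS and ORR are untouched. For MaxCombo, the SAP supports only a request to state whether the test is stratified.

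**What to change.** In Section 3.6.1.1, and by reference in 3.6.1.2, state that if RMST is run, the between-arm difference and its 95% CI will be estimated with the three randomization factors as covariates, by IPCW or pseudo-value regression. Keep the plain Kaplan-Meier areas by arm for display. As a clarification only, add whether the MaxCombo components use the same strata as the stratified log-rank test.

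The cost is a few sentences and one regression step in standard code. No new data are needed, and the sample size, alpha and primary analyses do not change.
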